### 5.2 Important steps for cohort formation

#### 5.2.1 Eligible cohort entry dates

Market availability of liraglutide in the U.S. started on January 20, 2010.

- For Marketscan: January 20, 2010-Dec 31, 2017 (end of data availability).
- For Medicare: Jan 1, 2012-Dec 31, 2017 (start- end of data availability).
- For Optum: January 20, 2010-March 31, 2019 (end of data availability).

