### 6.2 Preliminary covariates:

- Age
- Sex
- Combined Comorbidity Index (CCI), measured over the default baseline covariate assessment period, defined as 180 days prior to and including index date

Covariates listed above represent only a small subset of covariates that will ultimately be controlled for in the design and analysis. We use the covariates above only for initial feasibility analyses to judge whether there is likely to be sufficient overlap between treatment groups to proceed with the study. Remaining covariates are defined only after the study has passed the initial feasibility analysis and the initial power assessment and are listed in Table 1 (**Appendix B**). These covariates are based on those used by Patorno et al. (2019).

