## 9. Balance Assessment after PS matching

Action report name:

- For Liraglutide vs 2nd Gen. SUs

Optum: <https://bwh-dope.aetion.com/projects/details/632/results/44783/result/0>

Marketscan: <https://bwh-dope.aetion.com/projects/details/633/results/45436/result/0>

Medicare: <https://bwh-dope.aetion.com/projects/details/634/results/45432/result/0>

- For Liraglutide vs DPP4i

Optum: <https://bwh-dope.aetion.com/projects/details/632/results/44786/result/0>

Marketscan: <https://bwh-dope.aetion.com/projects/details/633/results/44787/result/0>

Medicare: <https://bwh-dope.aetion.com/projects/details/634/results/45433/result/0>

Date conducted: 11/18/2019 (Medicare 11/30/2019)

After review of initial feasibility and power analyses, complete creation of the remaining covariates (see Table 1 below for list of covariates). Again, using the dummy outcome of a 90-day gap in database enrollment, complete a 1:1 PS-matched analysis. The PS should include the complete list of covariates (excluding laboratory values, which are missing in some patients).

- Provide plot of PS distributions stratified by treatment group.

Note- Please refer to **Appendix B**.

- Report covariate balance after matching.

Note- For Table 1, please refer to **Appendix B**.

- Report reasons for censoring by treatment group.

- For Liraglutide vs DPP4i

	Overall	Referent	Exposure
Dummy Outcome	0 (0.00%)	0 (0.00%)	0 (0.00%)
Death	1,271 (0.75%)	827 (0.98%)	444 (0.53%)
Start of an additional exposure	4,700 (2.79%)	1,913 (2.27%)	2,787 (3.30%)

End of index exposure	99,981 (59.27%)	45,078 (53.44%)	54,903 (65.09%)
Specified date reached	29,951 (17.76%)	16,708 (19.81%)	13,243 (15.70%)
End of patient enrollment	22,798 (13.51%)	12,483 (14.80%)	10,315 (12.23%)
Switch to other SUs (for censoring) + nursing home admission	9,989 (5.92%)	7,336 (8.70%)	2,653 (3.15%)

- For Liraglutide vs 2nd Gen. SUs

	Overall	Referent	Exposure
Dummy Outcome	0 (0.00%)	0 (0.00%)	0 (0.00%)
Death	858 (0.79%)	595 (1.10%)	263 (0.49%)
Start of an additional exposure	4,294 (3.96%)	967 (1.78%)	3,327 (6.14%)
End of index exposure	61,038 (56.33%)	27,098 (50.01%)	33,940 (62.64%)
Specified date reached	21,830 (20.15%)	13,222 (24.40%)	8,608 (15.89%)
End of patient enrollment	14,181 (13.09%)	7,902 (14.58%)	6,279 (11.59%)
Switch to other SUs (for censoring) + nursing home admission	6,163 (5.69%)	4,398 (8.12%)	1,765 (3.26%)

- Report follow-up time by treatment group.

- For Liraglutide vs DPP4i

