...Males; n (%)	68,305 (49.6%)	9,191 (47.2%)	0.05	80,527 (56.2%)	10,789 (51.3%)	0.10	197,449 (43.4%)	19,778 (44.2%)	-0.02	346,281 (47.1%)	39,758 (46.6%)	0.01
...Females; n (%)	69,344 (50.4%)	10,269 (52.8%)	-0.05	62,810 (43.8%)	10,252 (48.7%)	-0.10	257,251 (56.6%)	25,000 (55.8%)	0.02	389,405 (52.9%)	45,521 (53.4%)	-0.01
Race												
...White; n (%)	N/A	N/A		N/A	N/A		337,843 (74.3%)	38,225 (85.4%)	-0.28	337,843 (74.3%)	38,225 (85.4%)	-0.28
...Black; n (%)	N/A	N/A		N/A	N/A		52,880 (11.6%)	3,806 (8.5%)	0.10	52,880 (11.6%)	3,806 (8.5%)	0.10
...Asian; n (%)	N/A	N/A		N/A	N/A		23,337 (5.1%)	531 (1.2%)	0.22	23,337 (5.1%)	531 (1.2%)	0.22
...Hispanic; n (%)	N/A	N/A		N/A	N/A		21,402 (4.7%)	801 (1.8%)	0.16	21,402 (4.7%)	801 (1.8%)	0.16
...North American Native; n (%)	N/A	N/A		N/A	N/A		2,392 (0.5%)	177 (0.4%)	0.01	2,392 (0.5%)	177 (0.4%)	0.01
...Other/Unknown; n (%)	N/A	N/A		N/A	N/A		16,846 (3.7%)	1,238 (2.8%)	0.05	16,846 (3.7%)	1,238 (2.8%)	0.05
Region - United (lumping missing & other category with West)												
...Northeast; n (%)	17,444 (12.7%)	1,756 (9.0%)	0.12	32,182 (22.5%)	3,998 (19.0%)	0.09	90,962 (20.0%)	7,000 (15.6%)	0.12	140,588 (19.1%)	12,754 (15.0%)	0.11
...South; n (%)	67,640 (49.1%)	10,376 (53.3%)	-0.08	34,576 (24.1%)	4,549 (21.6%)	0.06	193,471 (42.5%)	20,663 (46.1%)	-0.07	295,397 (40.2%)	35,587 (41.7%)	-0.03
...Midwest; n (%)	23,768 (17.3%)	3,839 (19.7%)	-0.06	59,121 (41.2%)	9,927 (47.2%)	-0.12	92,885 (20.4%)	10,345 (23.1%)	-0.07	175,774 (23.9%)	24,111 (28.3%)	-0.10
...West; n (%)	28,797 (20.9%)	3,490 (17.9%)	0.08	16,027 (11.2%)	2,339 (11.1%)	0.00	77,672 (17.1%)	6,770 (15.1%)	0.05	122,496 (16.7%)	12,599 (14.8%)	0.05
...Unknown/missing; n (%)	N/A	N/A	#VALUE!	1,431 (1.0%)	228 (1.1%)	-0.01	N/A	N/A	#VALUE!	1,431 (1.0%)	228 (1.1%)	-0.01
CV Covariates												
Ischemic heart disease; n (%)	39,052 (28.4%)	5,847 (30.0%)		46,475 (32.4%)	6,900 (32.8%)		148,750 (32.7%)	13,938 (31.1%)		234,277 (31.8%)	26,685 (31.3%)	0.01
Acute MI; n (%)	2,315 (1.7%)	293 (1.5%)		2,658 (1.9%)	311 (1.5%)		8,356 (1.8%)	541 (1.2%)		13,329 (1.8%)	1,145 (1.3%)	0.04
ACS/unstable angina; n (%)	2,694 (2.0%)	397 (2.0%)		3,152 (2.2%)	438 (2.1%)		9,368 (2.1%)	748 (1.7%)		15,214 (2.1%)	1,583 (1.9%)	0.01
Old MI; n (%)	5,390 (3.9%)	786 (4.0%)		3,482 (2.4%)	438 (2.1%)		19,366 (4.3%)	1,616 (3.6%)		28,238 (3.8%)	2,840 (3.3%)	0.03
Stable angina; n (%)	5,780 (4.2%)	956 (4.9%)		4,996 (3.5%)	757 (3.6%)		18,469 (4.1%)	1,724 (3.9%)		29,245 (4.0%)	3,437 (4.0%)	0.00

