Concomitant initiation or current use of SGLT2i; n (%)	2,699 (1.4%)	717 (5.7%)	1,961 (1.2%)	731 (5.3%)	4,774 (0.8%)	1,220 (4.3%)	9,434 (1.0%)	2,668 (4.9%)	-0.23
Concomitant initiation or current use of AGIs; n (%)	472 (0.2%)	22 (0.2%)	391 (0.2%)	29 (0.2%)	1,434 (0.3%)	83 (0.3%)	2,297 (0.2%)	134 (0.2%)	0.00
Concomitant initiation or current use of Glitazones; n (%)	12,440 (6.3%)	873 (7.0%)	12,991 (8.1%)	1,304 (9.4%)	28,770 (5.0%)	1,961 (6.9%)	54,201 (5.8%)	4,138 (7.6%)	-0.07
Concomitant initiation or current use of DPP4i ; n (%)	4,204 (2.1%)	109 (0.9%)	4,943 (3.1%)	124 (0.9%)	13,128 (2.3%)	225 (0.8%)	22,275 (2.4%)	#VALUE!	#VALUE!
Concomitant initiation or current use of Insulin; n (%)	6,048 (3.1%)	1,683 (13.5%)	5,661 (3.5%)	1,712 (12.4%)	22,161 (3.9%)	4,433 (15.5%)	33,870 (3.6%)	7,828 (14.3%)	-0.38
Concomitant initiation or current use of Meglitinides; n (%)	781 (0.4%)	86 (0.7%)	931 (0.6%)	215 (1.6%)	3,651 (0.6%)	402 (1.4%)	5,363 (0.6%)	703 (1.3%)	-0.07
Concomitant initiation or current use of Metformin; n (%)	105,292 (53.5%)	5,852 (46.9%)	83,840 (52.3%)	6,810 (49.3%)	296,366 (51.9%)	13,865 (48.6%)	485,498 (52.3%)	26,527 (48.4%)	0.08
Past use of SGLT2i ; n (%)	1,362 (0.7%)	294 (2.4%)	795 (0.5%)	249 (1.8%)	2,664 (0.5%)	540 (1.9%)	4,821 (0.5%)	1,083 (2.0%)	-0.14
Past use of AGIs; n (%)	186 (0.1%)	18 (0.1%)	131 (0.1%)	19 (0.1%)	576 (0.1%)	38 (0.1%)	893 (0.1%)	75 (0.1%)	0.00
Past use of Glitazones ; n (%)	4,080 (2.1%)	343 (2.7%)	4,296 (2.7%)	523 (3.8%)	9,151 (1.6%)	611 (2.1%)	17,527 (1.9%)	1,477 (2.7%)	-0.05
Past use of DPP4i ; n (%)	4,798 (2.4%)	474 (3.8%)	4,852 (3.0%)	747 (5.4%)	17,036 (3.0%)	1,321 (4.6%)	26,686 (2.9%)	2,542 (4.6%)	-0.09
Past use of Insulin ; n (%)	5,316 (2.7%)	999 (8.0%)	4,122 (2.6%)	1,028 (7.4%)	18,807 (3.3%)	2,604 (9.1%)	28,245 (3.0%)	4,631 (8.5%)	-0.24
Past use of Meglitinides ; n (%)	500 (0.3%)	60 (0.5%)	594 (0.4%)	96 (0.7%)	2,203 (0.4%)	188 (0.7%)	3,297 (0.4%)	344 (0.6%)	-0.03
Past use of metformin (final) ; n (%)	20,184 (10.3%)	1,473 (11.8%)	16,579 (10.4%)	1,760 (12.7%)	58,784 (10.3%)	3,377 (11.8%)	95,547 (10.3%)	6,610 (12.1%)	-0.06
Other Medications									
Use of ACE inhibitors; n (%)	95,481 (48.5%)	5,189 (41.6%)	75,829 (47.3%)	5,623 (40.7%)	267,223 (46.8%)	11,669 (40.9%)	438,533 (47.2%)	22,481 (41.0%)	0.13
Use of ARBs; n (%)	50,472 (25.7%)	4,265 (34.2%)	43,683 (27.3%)	5,149 (37.3%)	155,237 (27.2%)	10,277 (36.0%)	249,392 (26.9%)	19,691 (35.9%)	-0.19

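### Calendar year of cohort entry is not in the propensity score or in Table 1, so calendar time is not directly controlled and its balance between arms cannot be seen

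*Combined protocol and SAP*

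**What the plan says.** Section 6.2 starts from age, sex and a comorbidity index. It says that "Remaining covariates are defined only after the study has passed the initial feasibility analysis" and the initial power assessment, "and are listed in Table 1" of Appendix B. Section 9 then fixes the content of the final score: "The PS should include the complete list of covariates (excluding laboratory values, which are missing in some patients". Table 1, less laboratory values, is therefore the governing list.

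The demographic rows of Table 1 are age, sex, race (Medicare only) and region, for example "Region - United (lumping missing & other category with West". The other rows cover cardiovascular and diabetes history, other comorbidity, medication, laboratory values, comorbidity and frailty scores, and healthcare use. Neither comparison, before or after matching, has a row for year, quarter or date of entry.

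Sections 13.1 and 13.2 specify a Cox model in the matched cohorts. The trimmed analysis in Section 13.2 adjusts for deciles of the same score. No calendar stratum or covariate is named.

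Section 5.2.1 sets the entry windows:
- "For Optum: January 20, 2010-March 31, 2019 (end of data availability"
- "For Marketscan: January 20, 2010-Dec 31, 2017 (end of data availability"
- "For Medicare: Jan 1, 2012-Dec 31, 2017 (start- end of data availability"

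Appendix A defines outcomes by ICD-9 code and says that the lists were converted to ICD-10 with a mapping macro.

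**The concern.** Index date is known for every patient and precedes the outcome. Over six to nine years, event rates, background treatment and the recording of outcomes can all change. If the arms enter at different times within the window, such change becomes part of the estimated drug effect.

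The documents give reason not to presume a constant ratio of liraglutide to comparator starts. Entry opens on liraglutide's US market date in two of the three databases. Appendix A lists four other GLP-1 receptor agonists approved between April 2014 and December 2017. The coding of MI and stroke also changes system within the window.

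Reviewers are asked in Section 10 to judge balance between arms before the analysis proceeds. On this variable they have nothing to look at.

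**Working it through.** **1. Entry windows (Section 5.2.1) and share of matched DPP4i pairs (Section 10).**

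| Database | Window | Days / 365.25 | Pairs | Share of 84,345 |
|---|---|---|---|---|
| Optum | 20 Jan 2010 to 31 Mar 2019 | 9.2 years | 19,187 | 22.7% |
| MarketScan | 20 Jan 2010 to 31 Dec 2017 | 7.9 years | 20,777 | 24.6% |
| Medicare | 1 Jan 2012 to 31 Dec 2017 | 6.0 years | 44,381 | 52.6% |

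Only Optum reaches 2019. Medicare, with over half the pairs, starts two years after launch.

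**2. The plan's own power figure.** Pooled events against DPP4i are 2 × 84,345 × 21.67/1,000 = 3,655.5. The Schoenfeld formula at HR 0.87 and two-sided 0.05 gives Φ(√(3,655.5/4) × |ln 0.87| − 1.96) = 0.9878, which matches the stated 0.987775. The calculation has no calendar input, so reproducing it does not test this point. It does supply the precision: SE(log HR) = 2/√3,655.5 = 0.033, a 95% interval of about ±6.5%.

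**3. Is there indirect evidence on entry time?** SGLT2 inhibitors are a candidate marker, since the earliest approval date that Appendix A lists for the class is 29 March 2013. The Table 1 row is "Concomitant initiation or current use of SGLT2i; n" (%).

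| | Liraglutide | Comparator | Ratio |
|---|---|---|---|
| SGLT2i, unmatched, vs DPP4i | 3,801/85,279 = 4.5% | 15,318/735,686 = 2.1% | 2.1 |
| SGLT2i, unmatched, vs SU | 2,668/54,804 = 4.9% | 9,434/928,341 = 1.0% | 4.8 |
| Current insulin, unmatched, vs DPP4i | 9,742/85,279 = 11.4% | 29,538/735,686 = 4.0% | 2.8 |
| Current insulin, unmatched, vs SU | 7,828/54,804 = 14.3% | 33,870/928,341 = 3.6% | 3.9 |
| SGLT2i, matched, vs DPP4i | 3,699/84,345 = 4.4% | 3,733/84,345 = 4.4% | 1.0 |
| SGLT2i, matched, vs SU | 2,533/54,182 = 4.7% | 2,454/54,182 = 4.5% | 1.0 |

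Insulin is not a calendar marker, yet its ratios are of the same order. Endocrinologist visits show the same pattern before matching: 23.5% vs 10.6% against DPP4i and 23.8% vs 6.4% against SUs. The recomputed standardized difference for SGLT2i goes from −0.134 to 0.002 (DPP4i) and from −0.229 to −0.007 (SU). The marker therefore does not show that the arms enter at different times.

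**4. Possible size, by assumption only.** Let t be the annual hazard ratio of a secular trend and d the difference in mean entry year between arms after matching (positive if liraglutide is later). The bias factor on the HR is about t^d.

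| | d = 0.25 | d = 0.5 | d = 1 |
|---|---|---|---|
| t = 0.98 | 0.995 | 0.990 | 0.980 |
| t = 0.97 | 0.992 | 0.985 | 0.970 |
| t = 0.95 | 0.987 | 0.975 | 0.950 |

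If d is negative, the factors invert. With a true HR of 1, the chance of falsely showing benefit is Φ(|ln b|/0.033 − 1.96). It rises from 2.5% with no bias to about 5% at b = 0.99 and about 15% at b = 0.97. Neither t nor d comes from the documents.

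**The case against.** The strongest case against is that no imbalance has been shown. Both arms accrue in the same window and are matched within each database, so differences in calendar coverage between databases cannot confound the contrast. A reader might infer from the unmatched SGLT2i gap that liraglutide patients entered later. The documents do not support that: the gap fits heavier treatment and more specialist care equally well, and it is gone in the matched cohorts where the HR is estimated. The count of distinct diagnosis codes, which may partly track coding era, is also balanced after matching against DPP4i (6.95 vs 6.93, 2.39 vs 2.38 and 6.22 vs 6.18). Most of the assumed biases are smaller than the ±6.5% interval. The design diagram is not available in the text reviewed and might show something more.

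Much of this stands. There is no evidence of residual imbalance, and the size of any bias is conjecture. Three things do not follow:
- A shared window does not ensure the same distribution of entry dates within it.
- Balance on a drug used by about 4% to 5% of patients says little about entry year in the rest.
- The confidence interval describes sampling error and does not cover a systematic shift.

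On the diagram, Sections 6.2 and 9 make Table 1 the governing list.

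**Conclusion.** The omission is real: no step of the design or analysis handles calendar time, and Table 1 does not display it. The supported statement is that calendar time is not directly controlled and its balance is unknown. A reader might go further and conclude that secular trends or the coding change do bias the HR. That requires entry dates to differ between arms after matching, and the documents give no distribution of entry dates. Nor should 2010 to 2019 be read as the window for the whole study, since Medicare covers 2012 to 2017.

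Under the assumed trends and gaps above, the factor on the HR lies between 0.950 and 0.995, or the inverse, against a target effect of 13%. That is enough to justify using a baseline variable already in hand, but it does not show that the result would be wrong.

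**What to change.** Before the comparative analysis, for which Section 13 carries no date yet:
- Add index calendar year (or quarter) as a categorical PS term within each database, for both comparators.
- Re-run the 1:1 match.
- Add index year by arm and database to Table 1, before and after matching.
- Restate the matched N and power in Section 10, and repeat the balance review on the new match.

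The cost is one more covariate, a re-run and a second look at balance. Some pairs may be lost. The current match keeps 84,345 of 85,279 liraglutide patients (98.9%) against DPP4i and 54,182 of 54,804 (98.9%) against SUs. The unmatched comparator pools are 8.6 and 16.9 times as large (735,686/85,279 and 928,341/54,804). A small loss is therefore the reasonable expectation, but it cannot be computed without entry dates by arm.

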### 6.3 Outcome variables and study follow-up:

#### 6.3.1 Outcome variables

Effectiveness outcomes of interest (definitions provided in **Appendix A**):

- **Primary outcome:** 3-point major adverse cardiovascular events (MACE), i.e., non-fatal myocardial infarction, non-fatal stroke, or CV mortality
- Secondary outcomes: Individual MACE components:
  - Hospital admission for MI (for purposes of individual component, fatal MI is included)
  - Hospital admission for stroke (for purposes of individual component, fatal stroke is included)
  - All-cause mortality/CV mortality:
    - All-cause inpatient mortality identified using discharge status codes will be used as a proxy for “CV mortality” in commercial databases
    - Information on CV mortality through data linkage with the National Death Index (NDI) will only become available at a later date for Medicare and will be used in secondary analyses.

Control outcomes of interest (control outcomes only serve to assess aspects of study validity but are not further interpreted):

1. For comparison with 2nd Gen. SUs: Severe hypoglycemia (we expect to see protective effect; American Diabetes Association, 2018)

- A dosage change on the index treatment does not fulfill this criterion
- An added treatment that is not part of the exposure or comparator group does not fulfill this criterion (e.g. if a liraglutide user adds insulin, he or she does not get censored at the time of insulin augmentation)

For the ITT analyses, the censoring based on the augmentation/switching and treatment discontinuation will be replaced with a maximum allowed follow-up time of 365 days.

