##### Design Diagram – LEADER TRIAL REPLICATION

## 5. Cohort Identification

### 5.1 Cohort Summary

This study will involve a new user, parallel group, cohort study design comparing liraglutide to the DPP4 inhibitor (DPP4i) antidiabetic class as a proxy for placebo. Both 2nd generation sulfonylureas (SUs) and DPP4is are not known to have an impact on the outcome of interest. The comparison against DPP4i is the **primary comparison**. Initiators of 2nd generation SUs are used as a secondary comparator group. The patients will be required to have continuous enrollment during the baseline period of 180 days before initiation of liraglutide or a comparator drug (cohort entry date). Follow-up for the outcome (3P-MACE), begins the day after drug initiation. As in the trial, patients are allowed to take other antidiabetic medications during the study.

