## 6. Variables

### 6.1 Exposure-related variables:

#### Study drug:

The study exposure of interest is initiation of liraglutide. Initiation will be defined by no use of liraglutide or a comparator in the prior 6 months before treatment initiation (washout period).

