1	Type 1 diabetes	
Measured 180 days prior to drug initiation in any diagnosis position and inpatient or outpatient care setting
 
DM type 1 - At least 1 inpatient or outpatient ICD-9 Dx code of 250.x1 or 250.x3 or ICD-10 Dx code of E10.x in the 6 months prior to drug initiation.
	
Patorno, Elisabetta et al. "Cardiovascular outcomes associated with canagliflozin versus other non-gliflozin antidiabetic drugs: population based cohort study." BMJ 2018;360:k119 http://dx.doi.org/10.1136/bmj.k119
 
Patorno, Elisabetta et al. "Empagliflozin and the Risk of Heart Failure Hospitalization in Routine Clinical Care: A First Analysis from the Empagliflozin Comparative Effectiveness and Safety (EMPRISE) Study." Circulation. 2019 Apr 8. doi: 10.1161/CIRCULATIONAHA.118.039177

2	Use of a GLP-1 receptor agonist (exenatide, liraglutide or other) or pramlintide or any (dipeptidyl peptidase 4 (DPP-4) inhibitor within the 3 months prior to screening	
Dispensing of at least one of the following medications in the 90 days prior to drug initiation:
 
Use of a GLP-1 receptor agonist (exenatide, liraglutide or other) or pramlintide or any (dipeptidyl peptidase 4 (DPP-4) inhibitor within the 3 months prior to index date (Please see AHA therapy sheet.)
	

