Concomitant initiation or current use of Insulin; n (%)	1,423 (11.6%)	1,523 (12.4%)	1,389 (10.2%)	1,588 (11.7%)	4,047 (14.3%)	4,309 (15.2%)	6,859 (12.7%)	7,420 (13.7%)	-0.03
Concomitant initiation or current use of Meglitinides; n (%)	72 (0.6%)	84 (0.7%)	170 (1.3%)	207 (1.5%)	392 (1.4%)	398 (1.4%)	634 (1.2%)	689 (1.3%)	-0.01
Concomitant initiation or current use of Metformin; n (%)	5,832 (47.6%)	5,784 (47.2%)	6,814 (50.1%)	6,740 (49.6%)	13,754 (48.5%)	13,814 (48.7%)	26,400 (48.7%)	26,338 (48.6%)	0.00
Past use of SGLT2i ; n (%)	264 (2.2%)	278 (2.3%)	242 (1.8%)	236 (1.7%)	526 (1.9%)	530 (1.9%)	1,032 (1.9%)	1,044 (1.9%)	0.00
Past use of AGIs; n (%)	11 (0.1%)	18 (0.1%)	8 (0.1%)	19 (0.1%)	44 (0.2%)	38 (0.1%)	063 (0.1%)	075 (0.1%)	0.00
Past use of Glitazones ; n (%)	309 (2.5%)	338 (2.8%)	539 (4.0%)	512 (3.8%)	666 (2.4%)	606 (2.1%)	1,514 (2.8%)	1,456 (2.7%)	0.01
Past use of DPP4i ; n (%)	476 (3.9%)	463 (3.8%)	782 (5.8%)	738 (5.4%)	1,389 (4.9%)	1,313 (4.6%)	2,647 (4.9%)	2,514 (4.6%)	0.01
Past use of Insulin ; n (%)	966 (7.9%)	953 (7.8%)	930 (6.8%)	973 (7.2%)	2,565 (9.1%)	2,569 (9.1%)	4,461 (8.2%)	4,495 (8.3%)	0.00
Past use of Meglitinides ; n (%)	61 (0.5%)	60 (0.5%)	125 (0.9%)	90 (0.7%)	178 (0.6%)	187 (0.7%)	364 (0.7%)	337 (0.6%)	0.01
Past use of metformin (final) ; n (%)	1,455 (11.9%)	1,438 (11.7%)	1,789 (13.2%)	1,736 (12.8%)	3,446 (12.2%)	3,365 (11.9%)	6,690 (12.3%)	6,539 (12.1%)	0.01
Other Medications									
Use of ACE inhibitors; n (%)	5,063 (41.3%)	5,097 (41.6%)	5,527 (40.7%)	5,554 (40.9%)	11,457 (40.4%)	11,611 (41.0%)	22,047 (40.7%)	22,262 (41.1%)	-0.01
Use of ARBs; n (%)	4,202 (34.3%)	4,160 (34.0%)	5,158 (38.0%)	5,036 (37.1%)	10,227 (36.1%)	10,180 (35.9%)	19,587 (36.2%)	19,376 (35.8%)	0.01
Use of Loop Diuretics; n (%)	2,037 (16.6%)	2,076 (16.9%)	2,059 (15.1%)	2,080 (15.3%)	6,079 (21.5%)	6,171 (21.8%)	10,175 (18.8%)	10,327 (19.1%)	-0.01
Use of other diuretics; n (%)	501 (4.1%)	516 (4.2%)	565 (4.2%)	591 (4.3%)	1,463 (5.2%)	1,427 (5.0%)	2,529 (4.7%)	2,534 (4.7%)	0.00
Use of nitrates-United; n (%)	852 (7.0%)	864 (7.1%)	907 (6.7%)	968 (7.1%)	2,172 (7.7%)	2,226 (7.9%)	3,931 (7.3%)	4,058 (7.5%)	-0.01
Use of other hypertension drugs; n (%)	871 (7.1%)	875 (7.1%)	900 (6.6%)	899 (6.6%)	2,265 (8.0%)	2,241 (7.9%)	4,036 (7.4%)	4,015 (7.4%)	0.00
Use of digoxin; n (%)	176 (1.4%)	173 (1.4%)	182 (1.3%)	221 (1.6%)	623 (2.2%)	600 (2.1%)	981 (1.8%)	994 (1.8%)	0.00

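### Use of other GLP-1 receptor agonists 91–180 days before index is neither excluded nor in the propensity score, and the handling of such drugs when added in follow-up needs to be stated

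*Combined protocol and SAP*

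**What the plan says.** - **Exposure and comparator.** Section 6.1: "The study exposure of interest is initiation of liraglutide". The other GLP-1 RAs on the Appendix A drug sheet (exenatide, albiglutide, dulaglutide, lixisenatide, semaglutide) belong to neither study group. Section 5.1 describes the primary comparison as "comparing liraglutide to the DPP4 inhibitor (DPP4i) antidiabetic class as a proxy for placebo"; second-generation sulfonylureas (SUs) are the other comparator.
- **Washout.** Section 6.1: "Initiation will be defined by no use of liraglutide or a comparator in the prior 6 months before treatment initiation (washout period".
- **Exclusion 2, Appendix A.** For GLP-1 RAs, pramlintide and DPP4i the rule is "Dispensing of at least one of the following medications in the 90 days prior to drug initiation", restated as use "within the 3 months prior to index date". The trial column beside it has the same three months, counted from screening.
- **Propensity score.** Section 9 puts all Table 1 covariates except laboratory values into the PS. The SU version of Table 1 has a row "Past use of DPP4i ; n" (%), and both versions have a row for any pramlintide use. Neither has a row for GLP-1 RAs, past or current.
- **Follow-up.** Section 6.3 says of the augmentation criterion: "An added treatment that is not part of the exposure or comparator group does not fulfill this criterion". Its example is a liraglutide user who adds insulin. For the ITT analysis, "the censoring based on the augmentation/switching and treatment discontinuation will be replaced with a maximum allowed follow-up time of 365 days".

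**The concern.** At baseline, the two look-backs differ. A patient who used another GLP-1 RA between 91 and 180 days before starting liraglutide passes both the washout and Exclusion 2, and counts as a new user. In the trial, randomisation balances such history. Here only the PS can, and the variable is absent. Patients who have already tolerated the class are likely to be more common among liraglutide initiators than among comparator initiators, so the new-user contrast would be weakened mainly in one arm.

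In follow-up, the comparators stand in for placebo. If a comparator patient adds another GLP-1 RA and continues the index drug, the visible rule treats that drug as it treats added insulin, and events and time on it are counted as placebo-like. The study asks whether claims data reproduce a hazard ratio of 0.87 (Section 1.5), so unrecorded class use in either arm makes any discrepancy harder to interpret.

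**Working it through.** **1. The plan's own power figure.** Section 10, pooled liraglutide vs DPP4i: 2 × 84,345 × 21.67/1,000 = 3,655.5 events. With HR 0.87 and two-sided alpha 0.05, power = Φ(½√3,655.5 × |ln 0.87| − 1.96) = Φ(4.210 − 1.96) = 0.9878, which agrees with the plan. It is used only in step 5.

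**2. Exclusion 2 classes still present at baseline.**

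| Class barred for 90 days | Row in Table 1? | Remaining users, unmatched pooled |
|---|---|---|
| DPP4i (SU comparison) | Yes | liraglutide 2,542/54,804 = 4.6%; SU 26,686/928,341 = 2.9% |
| Pramlintide (DPP4i comparison) | Yes | liraglutide 54/85,279 = 0.06%; DPP4i 40/735,686 = 0.005% |
| GLP-1 RAs other than liraglutide | No | not reported |

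So a 90-day bar does leave users in the 180-day baseline, and for both reported classes they are more frequent in the liraglutide arm. After matching, past DPP4i use is 4.6% vs 4.9% (standardized difference 0.01): once the variable is in the PS, it balances.

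**3. Rough size of the unreported group (assumption).** In the DPP4i flowchart, prior liraglutide and DPP4i users are removed before Exclusion 2. The 953 + 963 + 1,652 = 3,568 patients it then removes are therefore mainly users of other GLP-1 RAs or pramlintide in the last 90 days. To guess how many 91–180 day users remain, borrow the DPP4i pattern in the SU comparison:
- past DPP4i users remaining: 26,686 + 2,542 = 29,228;
- removed by Exclusion 2: 7,666 + 8,727 + 23,001 = 39,394;
- ratio: 29,228/39,394 = 0.74 (0.64 to 0.80 by database).

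Then 0.742 × 3,568 ≈ 2,600 patients. If all were liraglutide initiators, that is at most about 3% of 85,279. The ratio is crude, because its denominator also contains GLP-1 RA and pramlintide users.

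**4. Censoring in Section 9.** The reasons sum exactly to the matched cohorts:
- DPP4i: 1,271 + 4,700 + 99,981 + 29,951 + 22,798 + 9,989 = 168,690 = 2 × 84,345;
- SU: 858 + 4,294 + 61,038 + 21,830 + 14,181 + 6,163 = 108,364 = 2 × 54,182.

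The rows are therefore exhaustive, and none names another GLP-1 RA. However, the DPP4i table has 9,989 patients in a row that combines switching to other SUs with nursing home admission. SUs are in neither group of that comparison, so the visible Section 6.3 rule does not explain the row.

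**5. Dilution in follow-up (assumption).** Let x be the share of referent time on another GLP-1 RA with the same hazard ratio of 0.87. The observed HR is 0.87/(1 − x + 0.87x) = 0.87/(1 − 0.13x).

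| x | Observed HR | Power at 3,655.5 events |
|---|---|---|
| 2% | 0.872 | 0.985 |
| 5% | 0.876 | 0.980 |
| 10% | 0.881 | 0.968 |

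The documents give no value for x. The nearest figure is the additional-exposure row of Section 9: 1,913/84,345 = 2.3% of DPP4i referents and 967/54,182 = 1.8% of SU referents. These are patients; the share of time after such a start would be smaller.

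**The case against.** The strongest points on the other side are these.

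- **The 90 days are the trial's own criterion**, and Section 5.2.2 aims to follow the trial as closely as possible. This stands. A reader might infer that the look-back should be lengthened to 180 days, but that would move the cohort away from the trial. The gap is the missing covariate.
- **The censoring text is incomplete in the copy reviewed.** The criterion that the Section 6.3 bullets qualify is not shown, which is no fault of the plan. The unexplained SU row suggests that the implementation may go beyond the visible rule. A reader might infer that starting liraglutide is the only class event that censors a referent, or that crossover is uncontrolled. The documents do not establish either. A referent who switches and stops the index drug is censored at the end of index exposure in the as-treated analysis; only add-on use is in question.
- **Section 5.1 allows other antidiabetic drugs during the study, as in the trial.** This stands as general permission. It does not say whether drugs of the exposure's own class are meant to count as background treatment in a placebo proxy.
- **The 3,568 patients were excluded.** Setting them against the liraglutide arm, 3,568/(85,279 + 3,568) = 4.0%, does not measure residual bias. It also mixes a count taken before Exclusions 3–20 with one taken after them.
- **Availability varies.** The drug sheet gives no approval date for exenatide. Semaglutide was approved on 5 December 2017, under four weeks before MarketScan and Medicare data end.
- **Indirect capture.** The naive-new-user flag and the count of distinct prescriptions carry some of the history, but do not identify the class.

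**Conclusion.** The baseline gap holds: 91–180 day use of other GLP-1 RAs is neither excluded nor in the PS, while the other two Exclusion 2 classes have Table 1 rows where relevant. Its size is not reported; about 3% of liraglutide initiators is an upper guess that rests on the borrowed DPP4i ratio and on all such patients being in that arm.

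The follow-up gap holds as a matter for reconciliation. The visible rule leaves add-on users of another GLP-1 RA on treatment, and no censoring row names them, but the full criterion is not visible. The expected effect is small: 0.87 reads about 0.872 to 0.881 for an assumed 2–10% of referent time, and power stays at 0.968 or above.

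A reader might infer a known bias toward 1, anti-conservative for noninferiority. The documents do not support that for the two problems together. Add-on use in referents pulls the HR toward 1, whereas liraglutide patients already selected for tolerating the class could push it down, so the net direction is unknown. Against a margin of 1.30 the dilution has no practical weight: at an observed 0.881, the expected upper 95% limit is about 0.881 × exp(1.96 × 2/√3,655.5) = 0.94. What is at stake is how a discrepancy from the trial result is interpreted.

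**What to change.** 1. Keep the 90-day exclusion. Add past use of GLP-1 RAs other than liraglutide, over the 180-day baseline, to Table 1 and the PS in both comparisons. Rerun the match before outcome analysis (the date field in Section 13 is blank) and report the counts by arm before and after matching.
2. Reconcile the Section 6.3 rule with the Section 9 implementation, including the SU row in the DPP4i comparison. State how other GLP-1 RAs are handled and report by arm how many patients start one while continuing the index drug.
3. In the as-treated analysis, or at least in a sensitivity analysis, count the start of any GLP-1 RA on the Appendix A sheet as an augmentation/switching event in both arms.

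The cost is one covariate from claims already held, a code-list edit and one rematch; eligibility does not change. Item 3 gives slightly less follow-up and may introduce informative censoring, which is a reason to report results with and without it. Item 3 does not affect the ITT analysis, which drops switching censoring by design.
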